COORDINATE-Diabetes is a cluster-randomized clinical trial to test the effectiveness of an innovative, clinic-level educational intervention to improve the management of patients with T2DM and CVD. The trial will be performed and interpreted in the context of clinical diabetes care in the U.S. using data from select electronic health record (EHR) sites. A subset of sites with EHR data available for querying in existing datamarts will be recruited to participate in two EHR-focused objectives: 1) to perform a baseline characterization of patients with T2DM and CVD, including demographics, treatment patterns and healthcare utilization such as hospitalization; and 2) to assist with the identification of patients eligible for the educational intervention trial.

What follows is the protocol for the COORDINATE trial; the objectives and planned analyses of data from EHR sites is summarized in section 8 of this protocol.

Table 1.Trial Summary Table

Patient-level Inclusion and Exclusion Criteria	Sites will be recruited based on sufficient patient volume, cardiologist and endocrinologist or diabetes care specialist commitment, and site capacity to perform the trial as well as ability to effectively communicate with the study team and patients. Attempts will be made to achieve geographic, investigator, and patient diversity.
	and cardiovascular disease as listed in the Inclusion Criteria.
	Patient Inclusion Criteria:
	1. Age ≥ 18 years old
	2. Diagnosis of Type 2 diabetes mellitus (T2DM) as reported in the patient's medical records.
	 3. History of at least one of the following conditions: a. Coronary artery disease (defined as prior MI, coronary revascularization (CABG or PCI), and/or obstructive CAD (≥50%) as documented by angiography or CTA) b. Stroke and/or carotid artery stenosis (≥50%) c. Peripheral Arterial disease (defined as claudication with ABI<0.9, prior peripheral revascularization, and/or amputation due to circulatory insufficiency)
	4. Baseline composite score of guideline recommended therapy of <3 at baseline entry into the trial. Patients would receive a score of 1 for each of the following care elements:
Site-Level Inclusion Criteria	 ACEi/ARB therapy High-intensity statin Most recent HbA1c<7% on metformin monotherapy 5. Ability to communicate with site staff and understand and provide written informed consent and proof of Health Insurance Portability and Accountability Act (HIPAA) authorization
	Patient Exclusion Criterion:

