1.2 Trial Outcomes

A variety of clinical, process of care, and implementation outcomes will be assessed in the trial. Primarily, we will measure whether our intensive education intervention successfully changes provider behavior and improves secondary prevention management in patients with T2DM and CVD by collecting and analyzing patient level data. Therefore, our outcomes will assess differences at the last follow-up visit in guideline-recommended therapy between the basic education and intensive education intervention groups.

Trial Objectives	Trial Outcomes		
Primary Objectives			
To test effectiveness of implementing a clinic- level multifaceted intervention that includes establishing cardiology and endocrinology partnerships and evidence-based care pathways to improve the medical management and care of patients with T2DM and cardiovascular disease.	The trial will examine the impact of the educational intervention on provider adherence to guideline-recommended therapy, which is the primary outcome, defined as the proportion of patients achieving guideline-recommended management for T2DM and CVD at the last follow-up visit, as initiated or confirmed by a cardiologist for all of the following (composite score of 3):		
	 Use of a regimen which includes an anti- hyperglycemic agent indicated and/or guideline recommended to reduce cardiovascular risk* a. Acceptable alternative: metformin monotherapy with HbA1c<7% Cuideline-recommended medical therapy* with ACEi/ARB Guideline-recommended medical therapy* with high-intensity statin: atorvastatin 40- 80mg daily OR rosuvastatin 20-40mg daily 		
	*As new consensus or evidence emerges and guidelines are updated, the composite score and requisites will be evaluated by the Steering Committee for needed updates on an ongoing basis. For the first component of the primary outcome (related to anti-hyperglycemic agents), patients will be evaluated according to the list of "indicated and/or guideline recommended" agents in effect at the time of their last follow-up visit . This decision was approved by the Steering Committee. Medications started during the study follow-up period that receive FDA indication/guideline recommendation during that time will count towards the primary outcome.		

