Secondary Objectives	It is important to note that the FDA indications and guideline recommendations will only become more liberal with time, not more restrictive. Of note, patients who are on any GLP1-RA or SGLT2i therapy at baseline will not be eligible for enrollment.		

Table 2.Trial Outcomes Table

All of the following secondary outcomes will be assessed at the last follow-up visit.

	 Assessment of cardiology provider behavior as measured by the following cardiologist-initiated medications for diabetes suggested by guidelines and FDA approved for CVD risk reduction: Proportion of patients achieving guideline-recommended therapy for T2DM Proportion of patients with an ACEi/ARB treatment Proportion of patient with a high-intensity statin treatment Variations on the Primary Outcome: Proportion of patients achieving a composite score of ≥ 2 Intermediate Outcomes: Changes from baseline to the last follow-up visit in the following: sBP, dBP, HbA1c, LDL-C Change from baseline to the last follow-up visit in proportion of patients achieving the following targets (individually and in combination): sBP<130 mmHg, dBP<80 mmHg, HbA1c<7%, LDL-C Clinical time-to-event outcomes (While the primary outcome will be measured as of the last follow-up visit, data on clinical outcomes will be collected throughout the follow-up period for each patient): Composite of all-cause death; hospitalization for: MI, stroke, decompensated heart failure, or urgent revascularization (coronary, peripheral, carotid) Each of the clinical time-to-event outcomes will also be assessed individually 		
Exploratory Objectives			
	The following may be assessed at up to 5 years in patients who have provided social security number information:		
	- all-cause mortality, as assessed by vital status obtained through the National Death Index		
Implementation Objectives			
	Provider-level implementation outcomes:		
	AcceptabilityAppropriateness		

Since assessing differences in clinical outcomes is not the primary objective of this study, clinical events will not be independently adjudicated.

2. Overall Design

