3.2.1 Guideline Recommended Management Endpoints

Secondary study objectives include assessment of the effect of the intervention on cardiologist provider behavior as measured by the individual components of the primary outcome and a variation of the primary outcome. We will also assess the effect of the intervention on the individual components of the primary outcome and a variation of the primary outcome by any provider. For each outcome listed below, we will determine whether the proportion of patients will be higher in the intervention than in the usual care arm. The secondary outcomes will be analyzed using the same methods as the primary outcome; a mixed-effects repeated measures logistic regression model with random intercepts for site to account for the effect of clustering, an unstructured covariance for repeated-measures overtime, an interaction for treatment by time, as well as adjustment for potential baseline factors as covariates including the baseline composite score (see Appendix 1, Section 8.1 for list). Given relatively a large number of pre-specified secondary components below, the 95% CIs on the ORs will be used in the interpretation of these findings, rather than p-values.

Guideline Recommended Management as Prescribed by Cardiologist Endpoints

- Proportion of patients prescribed by Cardiologist achieving guideline-recommended therapy for T2DM
- Proportion of patients prescribed by Cardiologist an ACEi/ARB treatment
- Proportion of patient prescribed by Cardiologist a high-intensity statin treatment
- Proportion of patients achieving a composite score of ≥ 2 prescribed by Cardiologist

Guideline Recommended Management by any Provider Endpoints

- Proportion of patients achieving guideline-recommended therapy for T2DM
- Proportion of patients an ACEi/ARB treatment
- Proportion of patient a high-intensity statin treatment
- Proportion of patients achieving a composite score of ≥ 2

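### The SAP counts ACEi/ARB and statin therapy prescribed by a cardiologist in all enrolled patients, whereas the protocol heads these outcomes cardiologist-initiated; carried-over prescriptions can dilute an effect on cardiologist behavior

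*SAP*

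**What the plan says.** Protocol Table 2 (section 1.2) introduces the first group of secondary outcomes as "Assessment of cardiology provider behavior as measured by the following cardiologist-initiated medications". The full phrase is narrower than the list beneath it: it reads "cardiologist-initiated medications for diabetes suggested by guidelines and FDA approved for CVD risk reduction", yet the bullets cover ACEi/ARB and high-intensity statin as well as T2DM therapy. Those bullets give plain proportions of patients on treatment and do not repeat the word *initiated*.

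SAP 3.2.1 states the aim as "assessment of the effect of the intervention on cardiologist provider behavior as measured by the individual components of the primary outcome". The corresponding endpoints are defined by prescriber, with no condition on when treatment began: "Proportion of patients prescribed by Cardiologist an ACEi/ARB treatment" and "Proportion of patient prescribed by Cardiologist a high-intensity statin treatment", plus T2DM therapy and a composite score of at least 2. A parallel set follows under "Guideline Recommended Management by any Provider Endpoints".

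Three other provisions matter:

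- **Entry.** Inclusion criterion 4 (Protocol Table 1) requires "Baseline composite score of guideline recommended therapy of <3 at baseline entry into the trial". Patients may therefore enter on ACEi/ARB, a high-intensity statin, or both. Current SGLT2i or GLP1RA users are excluded.
- **Denominator.** SAP 2.1 analyzes all enrolled patients.
- **Covariates.** SAP Appendix 1 (9.1) adjusts for the baseline composite score as a single 0 to 2 total. It lists neither same-drug status at baseline nor the baseline prescriber.

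**The concern.** The intervention can change what a cardiologist does for a patient who lacks a therapy. Audit and feedback (Protocol 4.2) is directed at enrolled patients who have not yet reached optimal care. For a patient already on the drug there is nothing to initiate.

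Under the SAP definition, a patient who entered on a cardiologist's ACEi/ARB and stays on it is a success in either arm. One treated by primary care is a failure in either arm unless a cardiologist takes over the prescription. Both kinds of patient add to the counts without showing whether cardiologists started more treatment. An odds ratio near 1 could then be read as no change in cardiologist behavior when cardiologists had in fact begun treating more untreated patients.

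The summed score only partly separates these patients. A score of 1 may mean ACEi/ARB alone, statin alone, or metformin monotherapy with HbA1c below 7%, and it never shows who prescribed.

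**Working it through.** **The plan's own figure.** The documents give no rate, power or sample size for these secondary endpoints. The primary-outcome design (SAP 1.3) is used below only for its cluster structure, and it reproduces. The design effect is 1 + (25 − 1) × 0.05 = 2.2, so effective n per arm is 21 × 25 / 2.2 = 238.6. Power for 10% versus 20% is then 86.7% (pooled normal formula) or 85.4% (noncentral t, 40 df), consistent with at least 85%.

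**Dilution: inputs, all assumed.**

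- b = share of patients on the drug at entry
- s = share of those prescriptions held by a cardiologist
- p = new cardiologist initiation among patients not on the drug: 0.10 basic arm, 0.20 intensive arm
- Prescriptions held at entry all continue, none changes prescriber, and b and s are equal in the two arms.

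**Formulas.** All-patient rate P = b·s + (1 − b)·p. Carried-over share of successes = b·s / P. The odds ratios are before covariate adjustment. Among patients off the drug at entry, OR = (0.20/0.80) / (0.10/0.90) = 2.25 for every b and s.

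| b | s | Basic | Intensive | OR | Carried-over share, basic / intensive |
|---|---|---|---|---|---|
| 0.3 | 0.25 | 14.5% | 21.5% | 1.61 | 52% / 35% |
| 0.5 | 0.3 | 20% | 25% | 1.33 | 75% / 60% |
| 0.5 | 0.5 | 30% | 35% | 1.26 | 83% / 71% |
| 0.7 | 0.5 | 38% | 41% | 1.13 | 92% / 85% |
| 0.7 | 0.75 | 55.5% | 58.5% | 1.13 | 95% / 90% |
| 0.8 | 0.5 | 42% | 44% | 1.09 | 95% / 91% |

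First row: 0.3 × 0.25 = 0.075 carried over; new treatment 0.7 × 0.10 = 0.07 or 0.7 × 0.20 = 0.14; totals 0.145 and 0.215; OR = (0.215/0.785) / (0.145/0.855) = 1.61.

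**Does the smaller denominator cost more than it gains?** Apply ICC 0.05 and 21 sites of 25 per arm to these endpoints (a further assumption), with no covariates and s = 0.5. Effective n per arm among patients off the drug is 525(1 − b) / [1 + (25(1 − b) − 1) × 0.05].

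| b | Power, all patients | Effective n, off drug at entry | Power, off drug at entry |
|---|---|---|---|
| 0.3 | 42% | 201.4 | 80% |
| 0.5 | 21% | 166.7 | 73% |
| 0.7 | 10% | 118.9 | 58% |

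In these cases the restricted comparison is the more informative one. Adjusting for the summed score would recover some of the all-patient loss; how much cannot be computed from the documents.

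**Imbalance with no effect.** If initiation is 10% in both arms but s happens to be 0.45 versus 0.55, the all-patient difference is 3 points at b = 0.3 (OR 1.19) and 7 points at b = 0.7 (OR 1.35). Randomization removes this in expectation, but with about 42 clusters a chance difference is possible.

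**T2DM endpoint.** With SGLT2i and GLP1RA users excluded, b is 0 for those drugs and this dilution does not arise. The metformin-monotherapy alternative (SAP 3.1) is the remaining route for carry-over.

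**The case against.** The strongest reply is that the SAP endpoint is a legitimate intention-to-treat proportion. In the example with 70% treated, 41% versus 38% is the correct effect in all enrolled patients, because a 10-point gain in 30% of them is 3 points overall. Patients treated at entry also inform continuation. This stands. The problem is dilution relative to the stated aim, and a reader who inferred that the outcome is misclassified would be going too far.

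A reader might also infer that the endpoint mostly reflects old prescriptions. The documents do not support that: they give no baseline drug or prescriber rates, and at the low end of the assumed range only 35% of intensive-arm successes are carried over.

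The protocol's own text is ambiguous. Its heading attaches *initiated* to diabetes medications, and nothing in it limits the denominator to untreated patients, so the restricted analysis proposed here cannot be presented as the protocol's definition. The primary outcome is worded "as initiated or confirmed by a cardiologist for all of the following (composite score of 3", and the SAP calls these endpoints components of that outcome, so a continued cardiologist prescription might be intended to count. If so, the SAP should say it, because the secondary heading does not include *confirmed*. The score of at least 2 sits in the protocol under variations on the primary outcome, not under the initiated heading.

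The any-provider endpoints do credit a patient well treated by primary care. They drop prescriber attribution, however, so they cannot measure cardiologist behavior.

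Finally, these are secondary endpoints that the SAP interprets through confidence intervals rather than p-values. That limits the consequence but does not remove it, since a diluted interval can still be misread.

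**Conclusion.** The point holds for the cardiologist-attributed ACEi/ARB and statin endpoints and, through them, for the cardiologist-attributed score of at least 2. The two documents describe these outcomes differently. The SAP version counts prescriptions that predate enrollment, and the planned covariates do not identify the drug or its prescriber.

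The expected consequence is dilution. Under the assumed inputs an initiation odds ratio of 2.25 becomes about 1.6 with 30% treated at entry and a 25% cardiologist share, and about 1.1 with 70% to 80% treated. These figures rest on assumed baseline rates, full continuation, no change of prescriber and no covariate adjustment. They show how far the effect could shrink and do not predict this trial's result.

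The cardiologist-prescribed T2DM endpoint is largely unaffected, and nothing here bears on the primary analysis. The change should be made, because it is cheap and the endpoints are meant to show whether cardiologists changed what they do.

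**What to change.** - **Wording.** Reconcile *initiated* (Protocol Table 2) with *prescribed by* (SAP 3.2.1). State whether a continued or taken-over prescription counts, and whether the protocol heading is meant to cover ACEi/ARB and statin.
- **ACEi/ARB and statin, cardiologist-attributed.** Analyze new cardiologist-initiated treatment by last follow-up among patients not on that therapy at baseline. Describe the restriction as an SAP choice made to match the stated aim.
- **All-patient proportions.** Keep them in the SAP Table 3 shell, adjusted for same-drug status at baseline rather than only the summed score.
- **Score of at least 2, cardiologist-attributed.** Adjust for which components were met at baseline. Restricting to entry scores of 0 to 1 would not remove carry-over: for a patient entering at 1, an old cardiologist prescription still supplies half of the success.
- **Data.** Confirm that prescriber is captured. Protocol Table 3 lists medications prescribed at each contact but no prescriber or initiation item, and the SAP endpoints already depend on knowing it.

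The cost is SAP text, a filter on baseline medication status (already collected) and extra baseline terms. The downside is a smaller denominator for two secondary endpoints. If prescriber is not being recorded, collecting it would be additional work, but the current definition needs it too.

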3.2.2 Intermediate Outcomes

A secondary objective of this trial is to assess whether the intervention will be associated with improvement from baseline on intermediate outcomes at last follow-up. Patients must have data at both time points to be included in the analysis.

For each of the continuous intermediate endpoints listed below, we will use a multivariable generalized mixed-effects linear model with random intercepts for site to assess the effect of the intervention after adjustment for potential baseline factors (see Appendix 1, Section 8.1 for list) including the baseline measure of each variable of interest. We will assess the relationship and the shape of association of each variable with the outcome and consider appropriate transformations for best fit. The unadjusted models will include intervention and the baseline measurement of variable of interest. Note, repeated measures model was not considered for the intermediate outcomes as labs were collected at only baseline and 12 months.

Continuous Intermediate Endpoints

- sBP at last follow-up
- dBP at last follow-up
- HbA1c at last follow-up
- LDL-C at last follow-up

For each of the binary intermediate endpoints listed below, we will use a multivariable mixed-effects logistic regression model with random intercepts for site to assess the effect of the intervention on reaching the target lab measure at last follow-up. We will adjust for potential baseline factors (see Appendix 1, Section 8.2 for list) including the interaction term in the model that is the interaction between the intervention and baseline achievement of target lab measure. The unadjusted models will include intervention and the baseline measurement of variable of interest.

Binary Intermediate Endpoints: Achieving targets at last follow-ups

- sBP<130 mmHg
- dBP<80 mmHg
- HbA1c<8%
- LDL-C<70 mg/dL
- Composite score of achieving all targets for sBP<130 mmHg, dBP<80 mmHg, HbA1c<8%, and LDL-C<70 mg/dL

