- Clinic visits: Patients in the intense intervention arm will be seen by their healthcare provider at baseline, either in clinic or via virtual visit, per local standard of care. Follow-up visits (i.e., standard of care in-person or virtual visit, or telephone call) will be conducted every three months by enrolling sites in the intervention arm. All patients in the intervention arm will have two to four follow-up visits, with a minimum of 6 months of follow-up. The overall length of follow-up will be 6 to 12 months. The date of the last follow-up visit will

be determined by the patient's enrollment date. Patient reported prescription data for medications of interest will be validated by sites via medical record collection. All data collected will be entered into an electronic data capture system. Clinic visits should be conducted as per standard of care.

• Labs: The following laboratory assessments are collected from the patient's electronic health record and are recommended as part of standard of care in all patients at baseline and at the last follow-up visit: basic metabolic panel, HbA1c, lipid panel. As part of standard of care, providers will be encouraged to also order a basic metabolic panel 1-2 weeks after each dosage change in ACEi/ARB, HbA1c every 3 months until it is <8%, and lipid panel 8 weeks after each statin dose titration. In summary, sites will be educated to guidelines and will not be mandated to collect specific labs at specific times from patients enrolled for the purpose of the study. Rather, the study will be collecting data including labs that have been performed as part of standard of care and are not required as part of the study.

In both study arms, we will evaluate and compare various methods to communicate with and engage patients throughout the study. These engagement efforts may focus on encouraging the patients to enroll/comply with study requirements, and/or may focus on encouraging the patient to be engaged in their own health care, knowledgeable about their disease state(s), and adherent to their medications.

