2.2 Missing Data

Operational efforts will be made to minimize missing data at baseline and during follow-up. Data quality checks will be built into the electric data capture system. Baseline and follow-up data will be reviewed on a regular basis and sites will be notified regarding any data quality concerns. DCRI study team will confirm with sites that missing data cannot be obtained. We anticipate negligible rates of missing data at baseline and follow-up as sites are conducting follow-up with their patients and electronic health system.

For the primary analysis, missing data for lab values and vital signs will be imputed to age and gender specific modes for categorical variables and medians for continuous variables. Missing data for medical history will be imputed to modes for categorical variables and medians for continuous variables. Missing medication data during follow-up will not be imputed, rather we will use a mixed-effects repeated measures model (MMRM) that effectively accounts for missing and correlated data within subject which is described in detail (Section 3.1)³. On indicated/guideline recommended therapy (yes/no) will be carried forward rather than the medication itself. Note, the intervention arm compared with usual care has additional follow-up at 3 and 9 months. This additional follow-up data will be used to help carry out the intervention through site audit and feedback reports, but will not be used as part of the primary outcome. Missing data may occur during follow-up due to a provider recommended temporary or permanent discontinuation of T2DM and CVD management in order to treat serious medical conditions, such

as leukemia. Rates of serious medical conditions should be similar by treatment arm. Missing data due to serious medical conditions will be treated the same as missing data for other known or unknown reasons. A sensitivity analysis will be conducted imputing missing last follow-up composite scores as failures. To better gauge the effect of truncating study follow-up time, we will conduct a sensitivity analysis that uses only 6-month outcome data.

3. Endpoints

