9.2 Potential Adjustment Variables for Binary Intermediate Outcome Models

Variable	Variable Type
Intervention	yes/no
Site: Urban vs. non-urban	yes/no
Age	continuous
Male sex	yes/no
Race	categorical (Black, Asian/Other, vs. White)
Baseline composite score	ordinal (0-2)
Charlson Comorbidity Index (CCI)	categorical (severe defined as CCI scores ≥ 5 , moderate defined as CCI scores of 3–4, vs. mild defined as CCI scores of 1–2)
**Achievement of Baseline HbA1c < 8%	yes/no
Achievement of Baseline systolic BP < 130 mmHg	yes/no
Achievement of Baseline diastolic BP < 80 mmHG	yes/no
**Achievement of Baseline LDL-C < 70 mg/dL	yes/no
Interaction* between intervention and achievement of baseline target	combination of intervention (yes/no) and achievement of baseline target (yes/no)

*For each outcome, we will test for interaction between intervention and achievement of that baseline target.

**Only the HbA1c and LDL-C outcomes will be adjusted for achievement of these Baseline metrics due to the rate of not drawn for these labs.

10. Appendix 2: Table Shells

Table 1. Patient-level Baseline characteristics by Intervention

PATIENT CHARACTERISTICS	Intervention	Usual Care
Age		
Sex		
Race: White Black Asian Other		
Ethnicity: Hispanic/Latino Not reported		
Insurance/payer: Medicare Part D Supplemental Plan Medicaid Private State-specific (non-Medicaid) Military health care Indian health services Other US insurance		
Medication prescription:		
Lipid lowering therapy: Statin: Low intensity Moderate intensity High intensity Ezetimibe Fibrate Niacin PCSK-9 Prescription-grade Omega 3 FA		
Glucose-lowering therapy: Metformin Insulin Sulphonylurea DPP4 Thiozolidinedione GLP-1RA SGLT-2		

Other Severity: Monotherapy > 1 glucose-lowering medication Average insulin dose		
Anti-hypertensive therapy ACE/ARB Beta-blocker Diuretic Calcium channel blocker MRA		
Anti-thrombotic therapy Aspirin P2Y12 receptor antagonist Warfarin DOAC		
Cardiovascular history		
Coronary artery disease Prior MI Prior CABG Prior PCI Obstructive ($\geq 50\%$) CAD (CT/ICA)		
Cerebrovascular disease: Prior ischemic stroke Carotid artery stenosis ($> 50\%$)		
Peripheral arterial disease: Prior peripheral revascularization Prior amputation due to poor circulation History of Claudication with ABI < 0.9		
Atrial fibrillation		
Heart failure		
Hypertension		
Dyslipidemia		
Cigarette smoking		
Non-Cardiovascular		
Charlson Index		
Diabetes history		
Time since diabetes diagnosis < 1 year		

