# of patients enrolled		
Location: Urban Non-urban		
Average baseline composite score (enrolled patients)		

Table 3. Effects of the Intervention on Guideline Recommended Medications

Analysis	No./Total (%) at last follow-up		Unadjusted		Adjusted	
	Intervention	Usual Care	OR (95% CI)	P-value	OR (95% CI)	P-value
Primary Outcome: Composite Score of 3						
Prescribed by Cardiologist: Achieving guideline-recommended therapy for T2DM ACEi/ARB treatment High-intensity statin treatment Achieving a composite score of ≥ 2						
Prescribed by Any Provider: Achieving guideline-recommended therapy for T2DM ACEi/ARB treatment High-intensity statin treatment Achieving a composite score of ≥ 2						

Table 4. Effects of the Intervention on Continuous Intermediate Endpoints at last follow-up

Analysis	Intervention			Usual Care			Unadjusted		Adjusted	
	Baseline N, Mean (SE)	Follow-up Mean (SE)	Difference	Baseline N, Mean (SE)	Follow-up Mean (SE)	Difference	Coefficient (SE)	P-value	Coefficient (SE)	P-value
sBP										
dBp										
HbA1c										
LDL-C										

SE- Standard Error

Population includes patients with data at both time points

Table 5. Effects of the Intervention on Achieving Targets at last follow-up

Analysis	Intervention		Usual Care		Unadjusted		Adjusted	
	Baseline No./Total (%)	Follow-up No./Total (%)	Baseline No./Total (%)	Follow-up No./Total (%)	OR (95% CI)	P- value	OR (95% CI)	P-value
sBP<130 mmHg dBP<80 mmHg HbA1c<8% LDL-C<70 mg/dL Composite score of achieving all targets								

Population includes patients with data at both time points

Table 6. Effects of the Intervention on Clinical time-to-first event endpoints within 12 months

Analysis	Cumulative Incidence (95% CI)		Unadjusted		Adjusted	
	Intervention	Usual Care	HR (95% CI)	P- value	HR (95% CI)	P- value
Composite of all-cause death; hospitalization for: MI, stroke, decompensated heart failure, or urgent revascularization (coronary, peripheral, carotid)						
All-cause death						
Hospitalization for MI						
Hospitalization for Stroke						
Hospitalization for decompensated heart failure						
Hospitalization for urgent revascularization						

11. Appendix 3: Figure Shells

Figure 1: Trial Population Flow Diagram

[figure not shown]

Figure 2: Changes in Composite Score and Components over time by Intervention

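### Limiting the LDL-C analyses to patients with both values may favour the intensive arm, because follow-up lipid testing can depend on statin titration differently by arm

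*SAP*

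**What the plan says.** SAP 3.2.2 sets the analysis set for all intermediate outcomes: "Patients must have data at both time points to be included in the analysis". The shells for Tables 4 and 5 in SAP Appendix 2 repeat it: "Population includes patients with data at both time points". The models adjust for the baseline value of the endpoint or, for the binary targets, for baseline attainment and its interaction with intervention. No model includes medication during follow-up.

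On how labs arise, Protocol 4.2 says that sites "will not be mandated to collect specific labs at specific times from patients enrolled for the purpose of the study". The same paragraph says that labs "are recommended as part of standard of care in all patients at baseline and at the last follow-up visit", and that providers will be encouraged to order "HbA1c every 3 months until it is <8%, and lipid panel 8 weeks after each statin dose titration". This paragraph stands among the intensive-arm activities. Protocol 4.1 has no such encouragement and says that basic-arm sites get no further instructions beyond the basic material. Contacts also differ: every three months in the intensive arm, at most two follow-up visits in the basic arm. Protocol Table 3 takes the most recent lab value in the record.

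On missing data, SAP 2.2 says "We anticipate negligible rates of missing data at baseline and follow-up". Yet the footnote in SAP 9.2 limits the use of baseline HbA1c and LDL-C attainment as covariates "due to the rate of not drawn for these labs". Neither place gives a rate. The median and mode imputation in SAP 2.2 is stated for the primary analysis, and its missing-data sensitivity analysis covers only the composite score.

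**The concern.** A complete-case comparison adjusted for baseline is sound if having a follow-up value depends only on variables in the model. Here a statin titration can itself prompt the lipid panel that supplies the follow-up value. Titration happens after randomisation, lowers LDL-C and is not in the model. If titration prompts testing more in the intensive arm, titrated patients are over-represented among that arm's tested patients. The LDL-C difference and the odds ratio for LDL-C below 70 mg/dL would then partly reflect who was tested. The all-targets composite inherits this through LDL-C and needs both labs, so it can lose the most patients. The plan has no analysis that would show the problem.

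**Working it through.** The plan gives no figure to reproduce here: no rate of missing follow-up labs, no titration rate and no design calculation for these endpoints. SAP 1.3 sizes the trial for the primary outcome only.

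**Which endpoints fit the mechanism**

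- LDL-C: the lipid panel is tied to statin titration, so it fits.
- HbA1c: the trigger is the HbA1c level (every 3 months until below 8%), not a dose change.
- sBP and dBP: vital signs, outside the lab encouragement.
- Basic metabolic panel: tied to ACEi/ARB dose changes, but not an intermediate endpoint.

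**LDL-C: inputs, all assumed**

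- D = 30 mg/dL, the fall in LDL-C if titrated
- t = share titrated: 0.30 intensive, 0.20 basic
- a, b = probability of a follow-up LDL-C if titrated and if not

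Titrated share among tested patients: s = t·a / [t·a + (1 − t)·b]. True difference = −D(t_I − t_B). Complete-case difference = −D(s_I − s_B). Bias is the second minus the first.

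True difference: −30 × (0.30 − 0.20) = −3.0 mg/dL.

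1. Only the intensive arm links testing to titration (0.85/0.60). s_I = 0.255/(0.255 + 0.420) = 0.378; s_B = 0.20. Difference = −30 × 0.178 = −5.3; bias −2.3.
2. As 1, with milder selection (0.80/0.70). s_I = 0.240/(0.240 + 0.490) = 0.329. Difference = −30 × 0.129 = −3.9; bias −0.9.
3. Both arms test at 0.85/0.60. s_B = 0.170/(0.170 + 0.480) = 0.262. Difference = −30 × (0.378 − 0.262) = −3.5; bias −0.5.
4. Titration 30% in both arms, so the true difference is 0; testing as in 1. Difference = −30 × (0.378 − 0.300) = −2.3; bias −2.3.
5. Titration 30% in both arms and testing at 0.85/0.60 in both. s_I = s_B; bias 0.

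If testing rates differ by arm but are unrelated to titration, s = t in each arm and the bias is 0.

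**Does baseline adjustment help?** A simulated baseline-adjusted regression was run with 525 patients per arm and no site clustering. Titration was 40% against 20% and independent of baseline LDL-C, with the same 30 mg/dL fall, so the true difference is −6.0. With intensive testing 0.90/0.70 and basic testing 0.70, s_I = 0.36/(0.36 + 0.42) = 0.462. The algebra gives −30 × (0.462 − 0.20) = −7.85, and the regression averaged −7.85. With 0.95/0.50 and 0.50, the algebra gives −10.8 and the regression −10.7. Adjustment removed essentially none of the bias. To the extent that baseline LDL-C predicts titration, it would remove some.

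**HbA1c.** The same kind of simulation used an assumed true effect of −0.20 and an intensive arm tested at 0.95 when HbA1c is 8% or above and 0.70 otherwise (basic 0.70). If the trigger is baseline HbA1c, the estimate is −0.20, without bias. If it is current HbA1c, the estimate is about −0.10, which is against the intervention.

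**The case against.** That the encouragement applies to the intensive arm only is inferred from where it is printed. The same paragraph recommends baseline and last-visit labs for all patients and treats the extra labs as standard of care. Basic-arm sites receive the cholesterol and diabetes guidelines too, and their clinicians may well check lipids after a titration. Because the most recent value counts, any routine panel can serve. This stands in part: it makes the -0.5 mg/dL case as plausible as the -2.3 case, and with equal titration the bias vanishes. It does not explain why the encouragement and the three-monthly contacts are written for one arm only.

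The footnote in SAP 9.2 might be read as an admission that follow-up labs are often missing. It is not: it concerns baseline values as covariates and gives no rate, and SAP 2.2 expects little missing data. It shows only that undrawn labs were enough of an issue to alter a covariate list.

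Requiring both values is a conventional choice for a change-from-baseline objective, and imputation also rests on an untestable assumption. Both are fair. They argue for showing the two analyses together rather than relying on one.

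**Conclusion.** The concern holds for LDL-C, for attainment of LDL-C below 70 mg/dL, and for the all-targets composite through its LDL-C component. These results may be biased toward the intervention. Under the main assumed inputs the size runs from about −0.5 mg/dL (both arms test titrated patients alike; zero if titration is also equal) to −2.3 mg/dL (only the intensive arm does). Larger assumed selection gives more: −4.8 on a true −6.0 in the strongest simulated case. None of these inputs is in the documents, and if few follow-up labs are missing the bias is negligible.

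A reader might infer that every intermediate effect is biased in favour of the intervention. The documents do not support that. HbA1c retesting follows the HbA1c level, so its bias may be nil or run the other way, which could also offset part of the effect on the composite. Blood pressure is untouched by this mechanism. Nor do the documents show that bias exists, only that the rule leaves room for it with nothing to detect it. These are secondary endpoints; the primary outcome is based on prescriptions and does not rest on this rule.

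**What to change.** For LDL-C, HbA1c, their targets and the all-targets composite, add to SAP 3.2.2 a prespecified multiple-imputation analysis, to be presented alongside the complete-case analysis:

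- impute separately by arm, accounting for site, which also respects the intervention-by-baseline interaction in the binary models;
- use baseline labs and vital signs, and statin intensity, ACEi/ARB and anti-hyperglycemic class at 6 months and the last visit, which Protocol Table 3 collects in both arms;
- include patients with either the baseline or the follow-up value missing;
- impute the continuous values and derive the targets from them.

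Report the share of patients with follow-up LDL-C and HbA1c by arm, and add these counts to the shells for Tables 4 and 5. State whether the median and mode imputation in SAP 2.2 applies to these endpoints, and reconcile its expectation of negligible missing data with the footnote in SAP 9.2.

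The cost is SAP wording and modest programming, with no new data collection. The downside is that the results depend on the imputation model, in particular on labs being missing at random given medication and the other variables in it.
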